2.2 General Considerations

Efficacy analyses will be performed by planned treatment (i.e. as randomized), and safety analyses by actual treatment received.

For continuous variables, descriptive statistics will include the number of subjects, mean, standard deviation (SD), standard error (SE), median, 25th and 75th percentiles, minimum and maximum.

For categorical variables, descriptive statistics will include frequencies and percentages in each category.

For time-to-event variables, the descriptive statistics will include the median, 95% CI, 25th and 75th percentiles, minimum and maximum. Counts (percentages) of subjects with events and of subjects censored will also be provided.

When mean change from baseline is summarized, subjects will only be included in the analysis if they have both a baseline value and a post-baseline value at the time point of interest.

Detailed statistical analyses are specified in sections below.

On June 24, 2021, sites were informed that the study would be closing and that subjects should be brought in for their End of Study (EoS) visit as soon as possible. After this date, many sites incorrectly began to titrate and/or discontinue blinded study drug medication prior to the EoS visit. Because this practice was wide-spread, data after June 24, 2021 will be censored for purposes of efficacy analyses. Sensitivity analyses, including data after June 24, 2021, will be conducted for the primary and key secondary endpoints. Safety and exposure analyses will primarily be conducted using all data. Some sensitivity analyses may be conducted using data only through June 24, 2021, as appropriate.

2.3 Subject Disposition

The number and percentage of subjects randomized, subjects who receive randomized study treatment, and subjects who complete study (or are terminated early) will be summarized by treatment group and overall. The number and percentage of randomized subjects terminating from the study early will be presented by reason. In addition, a summary of subject disposition as of June 24, 2021 will be provided.

The Randomized Set, FAS, and SS will be summarized by treatment group and overall.

The number and percentage of subjects who signed informed consent, screen failures and screen failure reasons will be summarized. The number and percentage of subjects in the Run-in phase, subjects who receive patiromer during the Run-in phase, and the reasons for the subjects not randomized at the end of the Run-in Phase will be summarized. Listings of subject disposition will be provided.

2.4 Protocol Deviations

Protocol deviations will be summarized for the Randomized Set. The number and percentage of subjects with protocol deviations will be summarized by category of deviation, separately for the Run-in Phase and the Blinded Treatment Phase, for each treatment group and overall. A listing of protocol deviations will be provided.

2.5 Demographics and Baseline Characteristics

Demographics will be summarized for the Randomization Set, the Full Analysis Set, and the Run-in Set. Baseline and screening characteristics will be summarized for the Randomized Set and the Full Analysis Set. Screening characteristics will be summarized for the Run-in Phase Set.

The summary of demographic information will include age, sex, race and ethnicity. The summary of patient characteristics at baseline will include, but is not limited to weight, height, body mass index, hyperkalemia status, prespecified medical history (for example, diabetes types, heart failure including New York Heart Association (NYHA) class, ejection fraction (EF), myocardial infarction, stroke, other arrhythmias, serum potassium, estimated glomerular filtration rate (eGFR)).

Listings of demographics and baseline characteristics will be provided.

2.6 General Medical History

General medical and surgery history will be coded in accordance with MedDRA 23.0 or an updated version and summarized for the Randomized Set, the FAS, and the Run-in Phase Set by body system (or procedure) for each treatment group and overall.

A listing of general medical history will be provided.

2.7 Study Drug Dosing and Compliance

The following summaries of exposure to blinded study drug (patiromer or placebo) will be provided for the SS, by treatment group:

- Duration: calculated as [last dose date]-[first dose date]+1.
- Total dose: calculated for each subject as the total dosage received
- Mean daily dose: calculated for each subject as the total dose divided by the duration of study drug exposure
- Number and type of titrations (up or down)
- Number of non-zero dose days

Treatment compliance will be calculated for each subject and summarized by treatment group. Dosing compliance will be derived from the total dose of study drug taken by a subject divided by the prescribed total dose over the treatment period, multiplied by 100. Descriptive statistics will be provided for dose compliance. The summary of study drug dosing and compliance will be presented separately for the Run-in and Double-Blinded Treatment Phases.

The primary exposure analyses will be conducted using all data. Sensitivity analyses may be conducted, using only the data through June 24, 2021.

A listing of all study drug dosing and compliance data will be provided.

2.8 Prior/Concomitant Medications and Procedures

All prior and concomitant medications including heart failure and RAASi drugs will be coded using the current version of the World Health Organization Drug dictionary (WHO Drug Global B3 March 2019). Prior and concomitant medications, including heart failure and RAASi drugs, will be separately summarized in the SS. Counts and percentages of subjects using each medication will be computed and summarized by treatment group.

Prior medications are medications with start date before the date of first dose of patiromer in the Run-in phase.

Summaries of concomitant medications will be provided separately for the Run-in and Double-Blinded Treatment Phases.

Concomitant medications during the Run-in Phase are medications with a start date on or before the end of the Run-in Phase and a stop date on or after the first patiromer dose date in the Run-in Phase, or no stop date at all. For subjects who were in the Run-in Phase twice, data from the second Run-in will be summarized. Data from the first Run-in will be included in listings only.

Concomitant medications in the Double-Blinded Treatment Phase are medications with a stop date on or after the first date of treatment in the Randomized Treatment Phase, or no stop date at all. Additional summaries may be provided for concomitant medications of interest.

Summaries of the percent of subjects at 100% and 50% of the target dose for ACEi, ARB, ARNi, MRA and beta blockers will be provided at Baseline, Day 3, and Weeks 1, 2, 6, and 18 for the Safety Set, by treatment group.

Listings of all prior and concomitant medications will be provided.

Listings of concomitant procedures will be presented.

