6.8.4 Concomitant Medications

Information on concomitant medication (prescription, over-the-counter, herbal and naturopathic remedies, etc.) will be collected beginning at Screening and continuing for the duration of the study (including EoS/ET Visit, Follow-up Phone Call, and Potassium Assessment Visit; see Section 8.5 and Section 8.6).

In general, subjects should continue on the same medications and regimens that were ongoing at the study entry with the exception of ACEi/ARB/ARNi and MRA medications (see Section 6.7.2). Doses of these concomitant medications should be kept as stable as

possible during the study. Medications that the Investigator deems indicated for treatment of any intercurrent illness or a pre-existing condition that are not on the prohibited medication list or do not form an exclusion criterion for participation in this study will generally be allowed.

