6.8.4.1 Permitted K⁺ Binding Medications

Only temporary use of sodium or calcium polystyrene sulfonate as well as sodium zirconium cyclosilicate is permitted for up to 7 days or until K⁺ is <5.0 mEq/L, whichever occurs first. During this period patiromer/placebo must be withheld. During the study, the Medical Monitor should be notified when a subject has been treated with K⁺ binding medications other than patiromer/placebo.

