8.4 EoS Visit Procedures

The common EoS date will be set by the Sponsor. The common EoS will occur when 820 subjects have completed the Week 6 visit. Recruitment will be stopped, and subjects called in by the sites for the EoS visit when it is projected that a sufficient number of subjects have been enrolled in order for 820 subjects to reach the Week 6 visit. All randomized subjects, including those who prematurely discontinued patiromer/placebo, will complete the EoS Visit within the timeline provided by the Sponsor around the common EoS date. Investigational sites will be notified of the study termination date as soon as possible after the decision is taken and should advise ongoing study subjects of the study termination date thereafter. All randomized subjects with final dose of patiromer/placebo within 1 week of the EoS Visit will complete a Potassium Assessment Visit within 2 weeks or as soon as possible thereafter to assess serum K⁺ levels and to collect AE data (see Section 8.6).

The following assessments will be performed at the EoS Visit:

- IWRS entry
- Perform KCCQ and EQ-5D-5L questionnaire (see Section 9.7)
- Assess NYHA class
- Perform physical examination
- Measure resting heart rate (pulse) after the subject has been sitting quietly for 5 minutes
- Measure blood pressure after the subject has been sitting quietly for 5 minutes (see Section 9.3.2)
- Measure weight
- Collect blood samples for evaluation of (see Table 5):
 - K⁺ level (measured locally and by central laboratory)
 - Serum chemistry including creatinine, eGFR (central laboratory)
 - Hematology (central laboratory)
 - BNP/NT-proBNP
 - High sensitivity troponin

- MRA level (see Section 9.2.1)
- Collect urine samples for the evaluation of (see Table 5):
 - Urinalysis
 - Assess urine ACR (see Section 9.6)
 - Urine or serum pregnancy test
- Assess AEs/special situations
- Record concomitant medications and procedures
- Investigational Pharmacist or qualified designee as assigned by the Principal Investigator performs drug accountability and collects all packets or kits dispensed during the Treatment Phase

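### SAP 2.8 sets no latest start date for Double-Blinded Treatment Phase concomitant medications, so drugs first started after the EoS/ET visit are tabulated by arm as blinded-phase use

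*SAP*

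**What the plan says.** SAP 2.8 gives one rule per phase.

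- **Run-in:** the rule covers "medications with a start date on or before the end of the Run-in Phase" that either stopped no earlier than initial patiromer dosing or have no stop date. Both ends are bounded.
- **Double-blind:** "Concomitant medications in the Double-Blinded Treatment Phase are medications with a stop date on or after the first date of treatment", or there is no stop date. Only the stop date is tested.

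The output is a table by arm in the Safety Set: "Counts and percentages of subjects using each medication will be computed and summarized by treatment group". No test is planned.

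Protocol 6.8.4 has medications collected from Screening for the whole study, "including EoS/ET Visit, Follow-up Phone Call, and Potassium Assessment Visit". Protocol 8.4 adds: "All randomized subjects with final dose of patiromer/placebo within 1 week of the EoS Visit will complete a Potassium Assessment Visit". It is due in the following 2 weeks, or at the earliest opportunity after that. Protocol 8.6 lists concomitant medications among that visit's assessments, without restriction. Protocol 8.7 limits the phone call to drugs used to treat an adverse event with onset up to 2 weeks after participation ended.

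I found no upper bound elsewhere. Protocol 12.7 separates only the periods before and after randomized treatment was received. SAP Appendix A only imputes partial dates. SAP 2.2 applies the 24 June 2021 cut-off to efficacy and bases safety and exposure analyses primarily on all data. SAP 2.8 states no cut-off of its own.

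**The concern.** A drug begun after EoS necessarily stops after the first blinded dose or has no stop date. It always satisfies the double-blind rule, so it is reported as use during a phase that was already over.

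This matters more here than in most trials. Remaining study drug is collected at EoS, so the patiromer arm loses an active binder while medications are still being recorded. During the study, other binders are tightly limited: "Only temporary use of sodium or calcium polystyrene sulfonate as well as sodium zirconium cyclosilicate is permitted for up to 7 days", with study drug withheld meanwhile. A longer-term binder started after EoS would sit in the blinded-phase table and could be read as on-trial rescue, or as use outside what the protocol permits. Starting a diuretic is also a listed hyperkalemia intervention (Protocol 4.1, Table 1), so new diuretic starts are open to the same misreading.

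For these two drug classes, no other by-arm summary is committed. SAP 2.8 says only that further summaries of medications of interest may be provided.

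**Working it through.** The plan gives no figure to reproduce on this point. The check has two parts.

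**1. The rule applied to example records.** Assume first blinded dose on Day 1, last blinded dose on Day 120 and EoS on Day 200.

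| Drug record | Rule as written | Start capped at EoS | Start capped at last blinded dose |
|---|---|---|---|
| Day -60 to Day -10 | not counted | not counted | not counted |
| Day 50 to Day 57 | counted | counted | counted |
| Day 150 to Day 157 (off drug, before EoS) | counted | counted | not counted |
| Day 210, no stop date (after EoS) | counted | not counted | not counted |

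The last row is the defect. The third row depends on intent: subjects who stop blinded drug remain in the study (Protocol 4.1 and 5.5.1), so this use still falls within the Treatment Phase. It is misplaced only if the table is meant to show on-treatment use.

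**2. Effect on the reported percentages.** Let p be the true proportion of users up to EoS and q the proportion of non-users who start the drug after EoS. The reported proportion is

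p' = p + (1 - p)q.

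Neither p nor q is in the documents. Assume p = 10% on placebo and 5% on patiromer (difference 5.0 points, ratio 2.00), with q from 0% to 20%.

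Worked line, q = 5% in both arms: placebo 0.10 + 0.90 x 0.05 = 14.50%; patiromer 0.05 + 0.95 x 0.05 = 9.75%; difference 4.75 points, ratio 1.49.

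| q placebo | q patiromer | Placebo | Patiromer | Difference (points) | Ratio |
|---|---|---|---|---|---|
| 0% | 0% | 10.00% | 5.00% | 5.00 | 2.00 |
| 5% | 5% | 14.50% | 9.75% | 4.75 | 1.49 |
| 10% | 10% | 19.00% | 14.50% | 4.50 | 1.31 |
| 20% | 20% | 28.00% | 24.00% | 4.00 | 1.17 |
| 5% | 10% | 14.50% | 14.50% | 0.00 | 1.00 |
| 5% | 15% | 14.50% | 19.25% | -4.75 | 0.75 |
| 10% | 5% | 19.00% | 9.75% | 9.25 | 1.95 |
| 15% | 5% | 23.50% | 9.75% | 13.75 | 2.41 |

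With equal q the difference is multiplied by (1 - q), so even at 20% it keeps 80% of its size (5.0 x 0.80 = 4.0 points) while the ratio falls much further. With unequal q the sign itself is not fixed.

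**The case against.** The case for leaving the text alone is that little can enter through this gap, and that what enters matters little.

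- **Narrow window.** The Potassium Assessment Visit falls about 2 weeks after EoS and the phone call asks only about adverse-event treatment. Nothing in the documents supports start rates of 5% to 20% in that time. This stands: the rates above are illustrations. The window is not empty, though. The visit records medications without restriction, and Protocol 10.5.4 asks for potassium above 5.0 mEq/L to be reported as an adverse event, so a binder begun for that reason could also be picked up by the call.
- **RAASi is covered elsewhere.** This stands. SAP 2.8 plans target-dose summaries at named visits, and RAASi use has its own endpoints. Protocol 5.4 requires every randomized subject to be on an MRA and an ACEi/ARB/ARNi already, so a dose change after EoS adds no new user; only a switch to a new agent would. An increased dose of a diuretic already in use likewise adds nothing.
- **Partial safeguards.** All medications are listed, and SAP 2.2 and 2.17 allow some sensitivity analyses through 24 June 2021. These are optional and do not change the main table.
- **The phase name implies a bound.** A programmer might apply one by convention. But the Run-in rule spells its bound out, so its absence from the neighbouring rule invites the literal reading.

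A reader might go further and infer that the arm comparison is diluted. That needs similar post-study start rates in both arms. The documents give no rates, and only one arm stops an active binder, so equality cannot be presumed.

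**Conclusion.** The point holds as a drafting defect with a definite consequence: applied as written, SAP 2.8 counts drugs first started after EoS/ET as blinded-phase use. That needs no assumption beyond such drugs being recorded, which the protocol provides for.

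The size and direction of the distortion cannot be determined. The percentages for newly started drugs, chiefly K+ binders and diuretics, can be inflated in either arm, and the contrast can move either way. If no subject starts a new drug after EoS, the effect is zero.

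A reader might also infer that efficacy conclusions are at risk. The documents do not support this. The primary analysis uses serum K+, the RAASi Use Score takes treatment status at the end of each pair's follow-up, and the main analyses of the primary and key secondary endpoints stop at 24 June 2021. The affected tables are descriptive. The correction is worth making because it is cheap and because these tables will be read as evidence on rescue use.

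**What to change.** In SAP 2.8, define Double-Blinded Treatment Phase concomitant medications as those with a start date on or before the EoS/ET visit and a stop date on or after the first date of blinded treatment, or no stop date. Put later starts in a separate post-study listing.

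The EoS/ET bound matches the phase, because subjects off blinded drug stay in it until EoS. If on-treatment use is what the table should show, say so and also flag starts after the last blinded dose.

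For K+ binders and diuretics, add the same table restricted to starts on or before 24 June 2021. SAP 2.2 records that many sites titrated or stopped study drug between that date and the EoS visit, and the EoS/ET bound alone would not separate those starts.

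The cost is one clause, one derivation flag and a repeat of the table for two drug classes. No new data are needed.

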2.9 Study Endpoints

Study PAT-CR-302 (DIAMOND Study) has the following primary endpoint:

- Changes in serum potassium levels from baseline

Hierarchical Key Secondary Endpoints:

1. Hyperkalemia events with a serum K^+ value >5.5 mEq/L
2. Durable enablement to stay on the MRA target dose (50 mg daily spironolactone or eplerenone), as assessed by the between-treatment-group difference of the cumulative frequency of subjects not staying on that target dose
Note: Discontinuation of the target dose for at least 14 days (or less if at the end of study) is required to confirm this endpoint.
3. Investigator reported events of hyperkalemia (first and recurrent)
4. Hyperkalemia related hard outcomes endpoints (Win Ratio)
 - a. Time to cardiovascular (CV) death
 - b. Total number of CV hospitalizations
 - c. Total number of hyperkalemia toxicity events with serum $K^+ >6.5$ mEq/L
 - d. Total number of hyperkalemia events with serum $K^+ >6.0-6.5$ mEq/L
 - e. Total number of hyperkalemia events with serum $K^+ >5.0-6.0$ mEq/L
5. RAASi Use Score (Win Ratio)

Other Secondary Endpoints:

- Durable enablement to stay on the target dose of ACE/ARB/ARNI, as assessed by the between-treatment-group difference of the cumulative frequency of subjects not staying on that target dose
Note: Discontinuation of the target dose for at least 14 days (or less if at the end of study) is required to confirm this endpoint.

- Durable hyperkalemia-free enablement to stay on the MRA target dose (days on 50mg MRA without presence of hyperkalemia)
- Total number of hyperkalemia toxicity events with serum $K^+ > 6.5$ mEq/L
- Total number of hyperkalemia events with serum $K^+ > 6.0-6.5$ mEq/L
- Emergency treatment for hyperkalemia (hospitalization or emergency room)
- Total number of hyperkalemia events with serum $K^+ > 5.0-6.0$ mEq/L
- KCCQ questionnaire, OSS, CSS and TSS during the treatment phase
- Investigator reported events of hyperkalemia (first event)
- Proportion of subjects on $\geq 50\%$ of target dose of ACEi, ARB, or ARNi and $\geq 50\%$ of target dose of MRA at the End of Study (EoS) Visit
- Time to first occurrence of CV death or CV hospitalization
- Time to MRA discontinuation
Note: Discontinuation of MRA, and no re-introduction after the event..
- Time to first occurrence of MRA discontinuation or death
- Time to ACEi/ARB/ARNi discontinuation
Note: Discontinuation of ACEi/ARB/ARNi, and no re-introduction after the event..

2.10 Statistical Assessment of Efficacy Endpoints

2.10.1 Primary Analyses

The primary analysis will be based upon the mean change in serum K⁺ levels from Baseline and is analysed by means of a mixed model for repeated measures (MMRM) approach. The model will include data through the last scheduled visit for which at least 10% of subjects have assessments.

The primary analysis will include only local laboratory serum potassium data from assessments on or before June 24, 2021. A sensitivity analysis will be performed that also includes data after June 24, 2021.

All analyses will be restricted to serum K⁺ assessments and not substituted by plasma values as they are known to be systematically lower. A Gaussian linear model for repeated measures will be used, with treatment, geographic region, sex, baseline T2DM status, and visit as factors, and baseline K⁺ level, baseline eGFR as covariates. The error terms are assumed to follow a multivariate normal distribution with unstructured covariance. Least squares mean changes from Baseline will be reported for both treatment groups with 95% CIs, as well as the difference between the least squares group means with 95% CI and p-value testing the null hypothesis of no treatment effect.

Changes in treatment effect over follow-up time will be explored by including treatment by visit interactions in the above-mentioned model. In addition, sensitivity analyses accounting for potentially informative missingness will be based upon a Win Ratio approach [1, 2].

The following additional sensitivity analyses will be conducted by re-running the primary MMRM as follows:

- Using local serum potassium data without a cutoff at June 24, 2021
- Using both local and central serum potassium data on or before June 24, 2021 (if both values are present at a visit, the centrally assessed serum potassium will be used)
- Using only central serum potassium data on or before June 24, 2021:

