6.7 Drug Dose Modification

6.7.1 Management of Serum K⁺

6.7.1.1 Management of Serum K⁺ in the Run-in Phase (Single-Blinded)

During the Screening Phase, subjects who satisfy the eligibility criteria will be enrolled into the Run-in Phase. The purpose of the Run-in Phase is for management of serum K⁺ with patiromer to allow optimization of RAASi medications (including initiation of MRA if not already receiving an MRA).

All subjects who meet the eligibility criteria for the Run-in Phase (single-blinded) will initiate patiromer (1 packet/day).

Subjects with 2 Screening K⁺ values >5.0 mEq/L are considered hyperkalemic; these subjects begin patiromer when they qualify for the Run-in Phase, i.e., on the same day Run-in qualification is met or the next day.

All other subjects are considered normokalemic and serum K⁺ will be measured again latest after the first week during the Run-in Phase. Patiromer will be started at this Week 1 Run-in Visit only if subjects are still normokalemic or have progressed to hyperkalemia; in case of newly observed hypokalemia (local serum K⁺ <4.0 mEq/L) during the first Run-in Week, patiromer must not be given. In subjects with hypokalemia serum K⁺ must be controlled after 3 days.

Note: If one screening K⁺ value is >5.0 mEq/L and one value is ≤5.0 mEq/L, then a third peripheral venipuncture is performed within 1 day to obtain clarity, whether subject is hyperkalemic or normokalemic (local serum K⁺ ≥4.0-≤5.0 mEq/L).

During the first Run-in Week, ACEi/ARB/ARNi and/or MRA doses ideally remain unchanged, if clinically indicated. On or after the initial first week visit during the Run-in Phase, up-titration of ACEi/ARB/ARNi and/or MRA may be initiated.

Patiromer is titrated during Run-in Phase to achieve target local serum K⁺ level of ≥4.0-≤5.0 mEq/L (see below).

Note: Depending on the actual local serum K⁺ value this could include patiromer 0 g/day (i.e., 0 packets/day) during the Run-in Phase.

- If local serum K⁺ is >5.0 mEq/L, up-titrate patiromer in at least (≥) 1-week intervals by 1 packet/day (maximum dose is 3 packets/day)
 - If subject is taking maximum dose patiromer (3 packets/day) and local serum K⁺ remains >5.0 mEq/L during the Run-in Phase, then subject is Run-in failed
- If local serum K⁺ is >5.0-≤5.5 mEq/L and the reduction in serum K⁺ from the previous visit was ≥0.4 mEq/L, at the Investigator's discretion, a dose increase may not be required

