12.2 Sample Size and Power Calculations

The sample size of 410 subjects per treatment arm (total of 820 subjects) has been calculated to provide 90% power to detect a difference between the control group (placebo) and the active group (patiromer) on the mean change in K^+ levels from Baseline. This sample size calculation was based upon the following assumptions: alpha level of 5% (2-sided), a difference between group means of 0.116, an SD of 0.5, and a 5% annual rate of loss to follow-up.

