1.2 Study Design

The DIAMOND study is a prospective Phase 3b multinational, multicenter, double-blind, placebo-controlled, randomized withdrawal, parallel group study that includes screening and an up to 12-week Run-in Phase (all subjects will have patiromer initiated and RAASi medications, including MRA, optimized) and a randomized withdrawal Double-Blinded Treatment Phase. The primary efficacy assessment will be based upon the data collected during the Double-Blinded Treatment Phase.

During the Run-in Phase, which is single blind to the subject, the Investigator will manage RAASi initiation and/or dose escalation as recommended by practice guidelines, using clinical judgment to customize RAASi addition or dose escalation based on subject response. Assessment of serum potassium will occur at each visit. The patiromer dose will be titrated based on the subject's potassium level.

After completing the Run-in Phase and found eligible for the Double-Blinded Treatment Phase of the study, subjects will be randomized. Randomized subjects will begin treatment with patiromer or placebo using the same number of packets established for patiromer at the end of the Run-in Phase and will continue the RAASi regimen being administered at the end of the Run-in Phase.

The study will continue until reaching at least the Week 6 visit for each subject. An independent Data Safety and Monitoring Board (DSMB) will act in an advisory capacity to monitor the safety of subjects who participate in this study.

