1.5 Sample Size

The sample size of 410 subjects per treatment arm (total of 820 subjects) has been calculated to provide 90% power to detect a difference between the control group (placebo) and the active group (patiromer) in change in K^+ levels from Baseline. This sample size calculation is based upon the following assumptions: alpha level of 5% (2-sided); difference between group means of 0.116; a SD of 0.5; and 5% loss to follow-up.

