2.15 Subgroup Analyses

Descriptive analyses (including the presentation of 95% confidence intervals) will be produced for the subgroups specified below for the primary and key secondary endpoints. These descriptive analyses will be summarized graphically through the use of forest plots.

The key subgroups to be analysed are:

- At screening, hyperkalemic vs normokalemic with a history of hyperkalemia
- BMI
- Ejection fraction (< versus \geq median observed value)
- AF ongoing at screening (Yes versus No)
- Ischemic vs non-ischemic
- Screening use of ARNi (Yes versus No)
- Screening use of MRA (Yes versus No)
- Screening comorbidity:
 - Diabetes mellitus (Yes versus No)
- Baseline comorbidity:
 - CKD stage
 - eGFR \geq 60 versus < 60
 - eGFR \geq 45 versus < 45
 - NYHA class (II vs III-IV)
- Region (D vs A, B, C)
- Sex (Male or Female)
- Age (< versus \geq median observed value)
- NT-proBNP at screening (\leq versus $>$ median observed value)

The following subgroups will also be analysed:

- History of AF (Yes versus No)
- Region
 - US vs Non-US
 - Georgia + Ukraine vs all other countries

Note: depending on actual patient recruitment, additional comparisons between other regions, e.g., Latin America, Western Europe, Eastern Europe, Japan may be conducted

- Age < 65 versus \geq 65
- Age < 75 versus \geq 75
- Age < 80 vs \geq 80

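### The primary MMRM leaves out two variables known before randomization, patiromer packets/day and Screening K+ status; this costs some precision but causes no bias

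*SAP*

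**What the plan says.** SAP 2.10.1 specifies a Gaussian repeated-measures model with treatment, "geographic region, sex, baseline T2DM status, and visit as factors", and with baseline K+ and baseline eGFR as covariates. Protocol 12.8.1 lists the same terms. None of the sensitivity re-runs in SAP 2.10.1 adds a baseline covariate; they change the laboratory source, the cut-off date, or the treatment-by-visit term. SAP 2.10.2 promises adjustment for relevant baseline characteristics, but it does so under the secondary endpoints and names no variables.

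On dose, Protocol 6.7.1.1 states: "Patiromer is titrated during Run-in Phase to achieve target local serum" K+ of 4.0-5.0 mEq/L, going up one packet at a time while K+ exceeds 5.0, to a maximum of three. Protocol 5.4 admits to randomization only subjects with local K+ of 4.0-5.0 mEq/L on at least one packet daily. SAP 1.2 then starts both arms "using the same number of packets established for patiromer at the end of the Run-in Phase".

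Randomization is stratified by region only (Protocol 12.3, SAP 1.3). Screening K+ status appears in SAP 2.15 as a descriptive subgroup: "At screening, hyperkalemic vs normokalemic with a history of hyperkalemia". Packets at randomization is in no listed subgroup.

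**The concern.** Baseline K+ is normally the strongest covariate in a change-from-baseline analysis of K+. Here it is measured on a dose chosen from the subject's own K+ and is confined to a window of 1.0 mEq/L. Two subjects can both enter at 4.7 mEq/L, one on one packet and one on three. They probably differ in underlying tendency to hyperkalemia, and the planned model sees them as alike unless eGFR, diabetes, sex or region separates them. In a withdrawal design the subject on three packets would be expected to rise more when switched to placebo.

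At stake is the width of the confidence interval for the primary comparison. Any outcome variance that packets and Screening status explain beyond the planned covariates stays in the residual. Dose is not a stratification factor either, so neither design nor analysis accounts for it.

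**Working it through.** **Step 1. Reproduce the plan's figure.** SAP 1.5 says that 410 per arm "has been calculated to provide 90% power to detect a difference", with "alpha level of 5% (2-sided); difference between group means of 0.116; a SD of 0.5; and 5% loss to follow-up".

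- n per arm = 2(z₀.₉₇₅ + z₀.₉₀)²σ²/δ² = 2 × (1.960 + 1.282)² × 0.25 / 0.116² = 390.4, so 391 evaluable.
- Allowing for 5% loss: 391/0.95 gives 412, and 391 × 1.05 gives 411. The stated 410 is reproduced to within 2 subjects.
- Power with 410 less 5% = 389.5 evaluable per arm: SE = 0.5 × √(2/389.5) = 0.0358; 0.116/0.0358 = 3.24; power = Φ(3.24 − 1.96) = 89.9%.

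The sample size is sound, and this point does not rest on an error in it. Protocol 12.2 words the loss as "5% annual rate of loss to follow-up" where the SAP gives no time base. That should be aligned, but it does not affect this point.

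**Step 2. Check that dose can carry information that baseline K+ lacks.** The Run-in rules were simulated with 400,000 subjects in each of seven scenarios. All inputs are assumptions: between-subject SD of underlying K+ 0.2-0.4, within-subject SD 0.3-0.45, and lowering per packet 0.06-0.20 mEq/L. Dose went up while measured K+ exceeded 5.0, and only subjects at 4.0-5.0 were kept. Change in K+ was then regressed on treatment and baseline K+, first without and then with the two variables.

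- Correlation of underlying K+ tendency with baseline K+: 0.20-0.50. With dose: 0.33-0.65. Dose was the stronger marker in every scenario, but baseline K+ kept part of the information.
- Added R²: 0.006-0.10 for dose alone and 0.018-0.16 for dose plus Screening status. In the four scenarios whose residual SD was near the plan's 0.5 (0.47-0.52), dose plus status added 0.018-0.109.
- The treatment estimate with and without the variables agreed to within 0.001.

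The simulation is generous in three ways. It has no eGFR or diabetes term to share the information. It has no dose or RAASi changes after randomization. It also treats Screening K+ as a direct reading of the same tendency. A working range of 0.02-0.10 is therefore used below.

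**Step 3. Translate added R² into precision.** Residual SD = 0.5 × √(1 − R²), with 389.5 evaluable per arm and δ = 0.116. This treats the comparison as one of two means, as the plan's own calculation does.

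| Assumed added R² | SE | SE reduction | Power | N per arm for 90% power, with 5% loss |
|---|---|---|---|---|
| 0 | 0.0358 | none | 89.9% | 412 |
| 0.02 | 0.0355 | 1.0% | 90.5% | 404 |
| 0.05 | 0.0349 | 2.5% | 91.3% | 391 |
| 0.10 | 0.0340 | 5.1% | 92.7% | 371 |

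The 95% CI half-width (1.96 × SE) goes from 0.070 at R² = 0 to 0.067 at R² = 0.10. The documents do not say whether the SD of 0.5 is raw or already covariate-adjusted; the table takes it as the residual SD under the planned model.

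**The case against.** The strongest reply is that nothing in the plan is wrong. Protocol and SAP prespecify the same model, which includes the only stratification factor and several prognostic covariates. What is missing is optional precision. That is right, and it sets the size of the point. Three stronger readings are tempting, and the documents support none of them.

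- *The omission biases the primary result.* Both variables are fixed before randomization, so leaving them out of a linear model neither biases the treatment difference nor inflates type I error. A chance imbalance in dose can move the estimate in a single trial, but the standard error already allows for it.
- *Titration empties baseline K+ of its information.* The information moves only in part. Packet count is itself noisy: one packet is compulsory for randomization, some dose increases and decreases are left to the investigator (Protocol 6.7.1.1), and randomization may occur at any time within 12 weeks.
- *The gain is large.* Figures above 10% of residual variance can be produced, but only from assumed dose mixes and per-packet slopes. Overlap with eGFR, diabetes and baseline K+ shrinks the gain. So does blinded-phase management: Protocol 6.7.1.2 requires an intervention above 5.5 mEq/L, which compresses differences in just the subjects with the highest tendency.

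The reply is also strong on Screening status. Normokalemic subjects qualify only if earlier hyperkalemia had led to a lasting RAASi reduction or discontinuation (Protocol 5.2). The status therefore partly records whether RAASi had already been cut, and Run-in then brings everyone to the MRA target dose and at least 50% of the ACEi/ARB/ARNi target. This makes packets the better candidate of the two.

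Finally, the SAP was finalised after the closure notice of June 24, 2021, and a late change to a primary model invites questions about covariate selection. That stands as a reason to fix the change while still blinded and to document it.

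**Conclusion.** The point holds as a modest improvement in precision, not as a defect that threatens the primary conclusion. Both documents omit the two variables, and the protocol's own titration and randomization rules explain why packet count should carry information that baseline K+ does not.

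Under an assumed added R² of 0.02-0.10, the standard error falls by about 1-5% and power rises from 89.9% to about 90.5-92.7%. That is worth about 8 to 41 subjects per arm (412 − 404 and 412 − 371). The low end is more likely, and with dose alone the gain could be close to nil. No figure in the documents fixes where in the range the trial lies. The planned 820 subjects, alpha and target difference are unaffected.

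**What to change.** Before unblinding:

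1. Add packets/day at randomization (1, 2, 3) and Screening K+ status (hyperkalemic or normokalemic) as factors in the primary MMRM of SAP 2.10.1 and in its re-runs. Define packets as the number assigned at Day 1/Baseline, and derive Screening status as for the SAP 2.15 subgroup. If only one is added, it should be packets.
2. Add packets at randomization to the SAP 2.15 subgroups, since the effect of withdrawal may plausibly differ by dose.
3. List the change from Protocol 12.8.1 in SAP section 3, with the reason.

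If the sponsor prefers to leave the primary model as it is, a prespecified supportive MMRM with the two factors is the lesser alternative.

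The cost is three degrees of freedom (two for packets, one for Screening status), SAP wording, and a documented departure from the protocol's model. No new data are needed.
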